9.5.3 Exploratory Analysis

Device use questions to support the human factors study of the delivery device will be performed as an exploratory analysis as described in the SAP. Any AEs, protocol deviations, or compliance issues identified in this study will be included in the primary analysis of this study and will be detailed in the main SAP.

9.5.4 Analysis of Safety

All safety analyses will be performed in the Safety Population.

The primary analysis of safety will include counts and proportions of participants with Aes and SAEs summarized by MedDRA System Organ Class (SOC) and Preferred Term (PT) and cross-tabulated by severity, relationship to study treatment, treatment received, and overall. Exact Clopper-Pearson 95% confidence intervals for proportions may be constructed.

All AEs and SAEs will be reported in a listing and events of interest will be itemized and listed separately.

9.6 Interim Analysis

Given the small number of expected events, there will be no interim analysis for efficacy. As described in Section 9.2, the enrollment may be closed when 18 cases are accumulated, but this will be considered the final analysis, not an interim analysis.

After every approximately 2,000 participants from the mITT cohort complete the study, the aggregated COVID case-rate will be used to calculate the projected number of cases for the full sample size of 11,480. The study may be considered futile if fewer than 10 cases are projected to be observed for the full sample size.

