7.13 Study Stopping Rules

A formal plan for interim data monitoring for futility will be established. Review of serious, unexpected, and related AEs by the CRO Medical Monitor, Data Safety Monitoring Board (DSMB), IRB, or HC/ FDA or applicable relevant local/national regulatory authorities may also result in suspension of further study agent administration. Health Canada/FDA/IRB/or local/national regulatory authority and study Sponsor(s) retain the authority to suspend additional enrollment and study agent for the entire study, as applicable.

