9.2 Determination of Sample Size

For an annualized infection rate of 3% in the placebo arm (daily incidence = 0.000075), and assuming a true hazard ratio of 0.15 implying protective effect of NONS equivalent to a vaccine efficacy of 85%, a sample size of 11,480 participants randomized 1:1 (NONS:Placebo) and available in the modified intent-to-treat (mITT) population will provide 90% power to demonstrate superiority of NONS to placebo in preventing COVID-19 infections reported through 28 days, based on Cox regression model and a 2-sided 0.05-level test (Schoenfeld 1983). The expected number of events in the two arms is 2 and 10 for the NONS and placebo groups respectively. This further assumes 25% censoring during the 28-day period (1.05% loss per day).

Sample size calculations conducted under version 1.0 of the protocol (dated April 27, 2021) used estimates of annualized case rates as listed in Table 2. At that time, the recent estimated annualized infection rate based on confirmed cases ranged from 2.2 through 3.9% in select Canadian provinces, though there was considerable variability, and these rates underestimate the true infection rates considering those untested. The US and other nations may have substantially higher infection rates and require fewer subjects to be randomized.

In particular, for the Czech Republic, Slovakia, and Sri Lanka, the reported annualized rates are between 0.14% and 8.23%, 0.07% and 7.27%, and 1.48% and 6.18% respectively over the period of May 1, 2021, to July 31, 2021. We are therefore likely to have sufficient power to conduct this study in those countries.

The maximum number of participants who will be randomized is 13,000, in order to achieve a maximum of 11,480 participants initiating their randomized treatment assignment and entering the mITT population. If the infection rate is higher than assumed here, enrollment and randomization will be closed if the total number of COVID-19 events in the mITT population exceeds 18 cases, 50% more than the number expected for 90% power. This inflation accounts for the increased infection rate and the consequent increased risk of infection between the time of randomization and time of initiation of study treatment due shipping times.

Table 2 Daily COVID-19 Counts

Population	Estimated annualized rate in February 2021	Equivalent date based on study in control arm	assumption	Days Daily Confirmed case counts exceeded 3% / 4% annualized rate		

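### Section 9.6 judges futility from a case count pooled over both arms, with a line of 10 against 12 expected cases, so it cannot tell low incidence from high efficacy

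*Combined protocol and SAP*

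**What the plan says.** Section 9.6 rules out an interim efficacy analysis but sets a recurring check after roughly every 2,000 mITT completers: "the aggregated COVID case-rate will be used to calculate the projected number of cases for the full sample size of 11,480". It then states: "The study may be considered futile if fewer than 10 cases are projected to be observed for the full sample size". No rate by arm enters the criterion.

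Section 9.2 sizes the trial at 11,480 for HR 0.15, and states: "The expected number of events in the two arms is 2 and 10 for the NONS and placebo groups respectively". Its claim that this sample size "will provide 90% power to demonstrate superiority of NONS to placebo" makes no allowance for a futility stop.

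Section 7.13 says: "A formal plan for interim data monitoring for futility will be established". Section 9.5.1 leaves termination criteria to the SAP, which Section 9.1 describes as a separate document. In the supplied text Section 9.6 is the only futility criterion, and no flag rates are given for it. Section 11.7 describes the DMC as reviewing safety data.

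**The concern.** The pooled count is placebo cases plus NONS cases. In a given epidemic it falls as NONS works better. A count below the line can mean that too few infections are occurring for the trial to answer its question, or that NONS is preventing them. Calling both cases futile treats a sign of success as a sign of failure. The line of 10 also lies only two cases below the total that the plan expects under its own alternative, so ordinary chance variation will cross it often, and the criterion is read up to five times before full size. If the flag were acted on, the trial could end in a setting where it would have succeeded.

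**Working it through.** **Inputs (Section 9.2 unless stated).** Placebo hazard h = 0.000075 per day; loss l = 0.0105 per day; 28 days; 5,740 per arm; design HR 0.15; two-sided 0.05. From Section 9.6: a look about every 2,000 completers, taken as 2,000, 4,000, 6,000, 8,000 and 10,000. Assumptions: 'aggregated' means pooled over arms, and each block of participants carries the plan's average event and loss rates.

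**The plan's own figures.** Schoenfeld events = 4(1.960 + 1.282)² / (ln 0.15)² = 11.68, rounded up to 12; 12 events give 91% power. Expected cases per arm = 5,740 × h/(h + l) × (1 − exp(−28(h + l))).
- Placebo: 5,740 × 0.007092 × 0.2563 = 10.43.
- NONS at HR 0.15: 1.57. Total 12.00, which matches the plan's 10 and 2.
- HR 1: 2 × 10.43 = 20.9. HR 0: 10.4.

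**What triggers a flag.** A look flags if cases × 11,480/n is below 10. That means at most 1, 3, 5, 6 or 8 cases at the five looks.

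**First look by hand.** At HR 0.15 the mean is 12.00 × 2,000/11,480 = 2.09, so P(≤1) = e^−2.09 × 3.09 = 38%. At HR 1 the mean is 3.64 and P(≤1) = 12%. The ratio is 3.1.

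**All five looks.** Poisson increments by arm, 400,000 simulated trials per scenario:

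| True HR | Expected total at 11,480 | Flagged at least once |
|---|---|---|
| 0 | 10.4 | 72.5% |
| 0.15 | 12.0 | 60.6% |
| 0.5 | 15.7 | 36.3% |
| 1 | 20.9 | 16.0% |

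The ratio of HR 0.15 to HR 1 is 60.6/16.0 = 3.8. The closure at 18 cases does not alter these rates, because a flag needs 8 cases or fewer.

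**Dependence on the background rate (HR 0.15 against HR 1).** Half the rate: 97% and 72%, ratio 1.3. Twice the rate: 9.6% and 0.6%, ratio 16. At 3%/365 = 0.0000822 per day: 52% and 11.5%, ratio 4.5.

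**What a flag means for the final test.** The score test succeeds if (placebo − NONS)/√total ≥ 1.96. At HR 0.15 and the plan's rate, 76.8% of trials are significant at full size: 43.2% significant and flagged, 33.6% significant and never flagged. So 43.2/60.6 = 71% of flagged trials would have been significant. At half the rate the share is about 45%. With exactly 9 cases in total, success needs 0 or 1 on NONS; with p = 0.15/1.15 that has probability 67%. By Schoenfeld, 9 events give 81% power.

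**Pooling or cut-off?** With the same pooled rule and a line of 5, flags at HR 0.15 fall to 18%, and power with every flag acted on rises from 34% to 65%.

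**By-arm alternative.** Flag if conditional power at 11,480 is below 10%, assuming HR 0.15 for remaining participants and the observed placebo rate. At the first look 1.82 placebo cases are expected, so P(0) = e^−1.82 = 16%. A literal zero rate projects no further cases and forces a flag.

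| | HR 0 | HR 0.15 | HR 0.5 | HR 1 | Power at HR 0.15, every flag acted on |
|---|---|---|---|---|---|
| Literal observed rate | 17% | 29% | 64% | 92% | 64% |
| Design rate until first placebo case | 3% | 19% | 61% | 92% | 72% |

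**The case against.** The check reads most naturally as a blinded screen for low incidence, and for that a pooled count is a sound tool. Section 9.2 quotes country rates from 0.07% to 8.23%, a range of more than 100-fold, whereas efficacy can move the pooled count at most two-fold. At one third of the assumed rate and HR 0.15 the rule flags 99.7% of trials, and full-size power there is only 29%, so it catches the case it seems meant for. The wording is permissive, Section 7.13 promises a formal plan, and Section 9.5.1 defers termination criteria to the SAP. Much of the damage also comes from placing the line at 10 when 12 are expected, and a lower pooled line would remove a good part of it without breaking the blind.

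All of this stands, and it limits the point. It does not remove it. The criterion as written calls a low pooled count futility, the line sits next to the plan's own success scenario, and no flag rates are given. A lower line reduces how often the flag misfires but still cannot say why the count is low.

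A reader might infer that the rule flags an effective spray four times as often as a useless one in general, or that it mostly ends trials that would have succeeded. The documents do not support either as a general statement: both hold only near the assumed rate. Nor is it a fault that an inactive spray would run on, since Section 9.6 excludes an interim efficacy analysis.

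**Conclusion.** The point holds in this form: a projection below 10 pooled cases is not in itself evidence of futility, and at the plan's own inputs it is met in about 61% of trials at HR 0.15 against 16% at HR 1. The direction was the same under every input tried; the ratio ran from 1.3 at half the assumed rate to 16 at twice the rate. Part of the problem is pooling and part is the closeness of 10 to 12.

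The fall in score-test power from 77% to 34% assumes that every flag stops the trial. A reader might take 34% as the trial's real power, or set it against the 90% in Section 9.2. Neither follows. The rule says 'may', so these are probabilities of meeting the criterion and not of stopping, and the like-for-like baseline is the 77% from the same score test with no stop. The results also rest on reading 'aggregated' as both arms together and on five looks.

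**What to change.** In Section 9.6, relabel the pooled projection as a blinded event-accrual check used for planning enrolment, and state that fewer than 10 projected cases is not in itself a ground for futility.

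If a futility stop is kept, have an unblinded statistician give the DMC the case counts by arm at the same looks. The DMC would make a non-binding recommendation to stop only if conditional power at 11,480 is below 10%, assuming HR 0.15 for remaining participants and the observed placebo rate. The design placebo rate should be used until the first placebo case occurs; without that provision the rule performs clearly worse, as the second table shows. State the chosen rule's flag rates at HR 0.15 and HR 1 next to the power claim in Section 9.2.

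Cost: rewording of Section 9.6, the SAP and the DMC charter, and a small closed-session table at each look. Unblinded CRO staff already exist (Section 5.5). No participants, visits or alpha are added. The real downside is a new function for the DMC: Section 11.7 gives it safety data only, and it would now see by-arm case counts and have to meet at these looks, which its charter must say. Relabelling alone avoids that cost.

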10 QUALITY CONTROL AND ASSURANCE

10.1 Regulatory and Ethical Considerations

This study will be conducted in accordance with the protocol and with the following:

- Consensus ethical principles derived from international guidelines including the Declaration of Helsinki and Council for International Organizations of Medical Sciences (CIOMS) International Ethical Guidelines
- Tri-Council Policy Statement: Ethical Conduct for Research Involving Humans TCPS 2 (2018)
- International Council for Harmonisation (ICH) E6 (R2) Guideline for Good Clinical Practice
- Food and Drug Regulations Part C, Division 5 Drugs for Clinical Trials Involving Human Participants
- Health Canada 's Management of clinical trials during the COVID-19 pandemic: Notice to clinical trial Sponsors
- Regulations of all other jurisdiction where the trial is undertaken, eg, with respect to the EU, all applicable laws and regulations of a member state where the trials is undertaken, especially those transposing and implementing Directive 2001/20/EC of the European Parliament and of the Council of 4 April 2001 on the approximation of the laws, regulations and administrative provisions of the Member States relating to the implementation of good clinical practice in the conduct of clinical trials on medicinal products for human use. Or the Regulation EU No 536/2014 of the European Parliament and of the Council on clinical trials on medicinal products for human use should it become effective in term of the present Agreement. Plus the Regulation (EU) 2016/679 on the protection of natural persons with regard to the processing of personal data and on the free movement of such data, and repealing Directive 95/46/EC (General Data Protection Regulation), and if in the United States, regulations 21 Code of Federal Regulations (CFR) 50, 56 and 312.
- The protocol, protocol amendments, ICF, Investigator Brochure, and other relevant documents (e.g., advertisements) must be submitted to an IRB/IEC by the Investigator and reviewed and approved by the IRB/IEC before the study is initiated.
- Any amendments to the protocol will require IRB/IEC approval before implementation of changes made to the study design, except for changes necessary to eliminate an immediate hazard to study participants.

The Investigator will be responsible for the following:

- Providing written summaries of the status of the study to the IRB/IEC annually or more frequently in accordance with the requirements, policies, and procedures established by the IRB/IEC
- Notifying the IRB/IEC of SAEs or other significant safety findings as required by IRB/IEC procedures

Providing oversight of the conduct of the study at the site and adherence to requirements of Food and Drug Regulations Part C, Division 5 Drugs for Clinical Trials Involving Human Participants, in particular the undertakings and practices described in: C.05.012(3)(f) (Qualified Investigator Undertaking) and C.05.010 concerning Good Clinical Practices.

Therapeutic Product's Directorate Guideline for Good Clinical Studies, Guidance Document: Part C, Division 5 of the Food and Drug Regulations "Drugs for Clinical Trials Involving Human Participants" (GUI-0100) – Summary or all other applicable local regulations e.g. US regulations 21 CFR 312. 60-68.

10.1.1 Data Protection

- Participants will be assigned a unique study number. Any participant records or datasets that are transferred to the Sponsor will contain the identifier only; participant names or any information which would make the participant identifiable will not be transferred.
- Only participant data will be analyzed during the study.
- The following emergency contact data will be collected: informed consent, name, and telephone number.
- The participant must be informed that his/her personal study-related data will be used by the Sponsor in accordance with local data protection law. The level of disclosure must also be explained to the participant who will be required to give consent for their data to be used as described in the ICF.
- The participant must be informed that his/her medical records may be examined by Clinical Quality Assurance auditors or other authorized personnel appointed by the Sponsor, by appropriate IRB/IEC members, and by inspectors from regulatory authorities.

10.1.2 Dissemination of Clinical Study Data

Following completion of the study, the data may be considered for publication in a scientific journal or for reporting at a scientific meeting. The Investigator is obligated to keep data pertaining to the study confidential. Archiving per country specific requirements (eg, 25 years in Canada).

10.1.3 Auditing and Inspecting

The study may be evaluated by representatives of the Health Canada, and where applicable, other government agencies, national health agencies, and national health authorities, who also will be allowed access to study documents. The Investigator and regional centers should promptly notify the Sponsor when any inspections are scheduled, as well as providing the results of any unscheduled investigations performed by any regulatory authorities.

The Investigator and regional centers will permit study related monitoring, audits, and inspections by the IRB/EC, the Sponsor, government regulatory bodies, and compliance and quality assurance groups of all study related documents (eg, source documents, regulatory

documents, data collection instruments, study data, etc.). The Investigator will ensure the capability for inspections of applicable study-related facilities. All authorized personnel, including health authority inspector(s), Sponsor and designees, Study/CRO Medical Monitor(s), Data Monitoring Committee (DMC) members, and auditor(s) will be given direct access to source data and documentation (eg, medical records, laboratory results, etc.) for source data verification, provided that participant confidentiality is maintained in accordance with local requirements.

Participation as an Investigator in this study implies acceptance of potential inspection by government regulatory authorities and applicable compliance and quality assurance offices.

11 ADMINISTRATIVE CONSIDERATIONS

11.1 Institutional Review Board (IRB) or Independent Ethics Committee (IEC) Approval

The Investigator, sub-Investigator, and regional centers will provide the ethics review board (eg, IRB or IEC) with the study protocol, the ICF, all written materials for the participant, and all advertisements used for participant recruitment. No participants are to be enrolled in the study until the IRB/IEC provides written approval of the protocol and the ICF, and not until approval documents have been sent to the Investigator and copies received by the Sponsor. All reviews will be in accordance with GCP. The IRB will be notified of any SAEs reported on the study. Appropriate reports on the progress of the study will be made by the Investigator to the IRB/IEC and to the Sponsor in accordance with the applicable government regulations, and in agreement with the policy established by the Sponsor.

11.2 Ethical Conduct of the Study

The study will be conducted in accordance with GCP requirements as described in the current revision of the International Council for Harmonisation (ICH) of Technical Requirements for Pharmaceuticals for Human Use guidelines and all applicable regulations, including the current Canadian Food and Drug Regulations Part C, Division 5 in particular C.05.010, US Code of Federal Regulations (CFR), Title 21, Parts 50, 54, 56, and 312, and Title 45, Part 164. Compliance with these regulations and guidelines will also constitute compliance with the ethical principles that have their basis in the Declaration of Helsinki and as outlined in the Tri-Council Policy Statement: Ethical Conduct for Research Involving Humans – TCPS 2 (2018). This study will also be carried out in accordance with local legal requirements in each participating country.

11.3 Participant Information and Consent

Each participant will be provided a written ICF (electronic or hard copy), describing this study and providing sufficient information to make an informed decision about participation in this study. The participant will be given opportunities to discuss and review the study requirements with a regional representative for their location. Copies of completed consents, will be provided back to the participant (digitally or hard copy) based on the email address provided by the participant or in-person during the on-site visit.

A copy of the proposed ICF must be submitted to the Sponsor and/or designee for review prior to submission to the reviewing IRB/EC. The ICF must be approved by the IRB/EC and must contain all elements required by federal, provincial, state, local, and institutional regulations or requirements. Canadian institutions must comply with all applicable federal and provincial privacy legislation (see Section 11.5).

Institutions in the US must be in compliance with Health Insurance Portability and Accountability Act of 1996 with regard to obtaining authorizations for use and disclosure of Protected Health Information. Local privacy regulations must be followed, including the

General Protection Data Regulation (GDPR) applicable in the EU. For Canada, see Section 11.4 regarding legal obligations for privacy and confidentiality of personal information.

The study, including its goals, methods, expected benefits, and potential hazards will be completely explained to each prospective study participant. It will also be explained to participants that they are free to refuse entry or to withdraw from the study at any time without prejudice to future treatment. Voluntary informed consent must be obtained from each eligible participant (and/or legally authorized representative if the participant is mentally incompetent or physically incapacitated) before any protocol-defined procedures are performed.

The participant's willingness to participate in this study will be documented on the IRB/EC approved ICF which must be signed and dated by the participant or legally acceptable surrogate, and the physician Investigator (Principal or sub-Investigator). The Investigator will keep the original ICF, and a copy will be given to the participant. The process for obtaining informed consent should also be noted in the participant's source documentation.

11.4 Patient Confidentiality

The Investigator, sub-Investigator, and regional centers must assure that the privacy of the participants, including their identity and all personal medical information, will be maintained at all times. In the eCRFs and other documents (eg, laboratory reports, etc.) submitted to the Sponsor, participants will not be identified by name, but by an identification code (eg, participant identification numbers). Remote monitoring may involve either a redacted source document or remote review of unredacted source document, per CRO and/or institutional polices. All Non-Canadian institutions must comply with all applicable national and regional privacy legislation. Canadian institutions must comply with all applicable federal (Personal Information Protection and Electronic Documents Act) and provincial privacy legislation eg,:

- BC Personal Information Protection Act, Freedom of Information and Protection of Privacy Regulations, BC eHealth Act,
- Alberta Personal Information Protection Act
- Ontario Personal Health Information Protection Act
- Quebec Loi sur la protection des renseignements personnels dans le secteur privé

Personal medical information may be reviewed for the purpose of verifying data recorded in the CRF by the Study/CRO Medical Monitor, Sponsor or designee, or regulatory authorities. Personal medical information will always be treated as confidential. Personal data is also protected in accordance with the personal data privacy legislation in each participating country, per the General Protection Data Regulation (GDPR) applicable in the EU.

